1.4 Correlative Objectives

1. Determine the association between responses at 6 months and the changes in the plasma levels of various proteins and cytokines (ST2, SPON1, CXCR3, CXCL10, IFN gamma, soluble IL-2R, IL-2, IL-4, IL-5, IL-6, IL-12, TNF- α , TRAIL/TNSFSF10/7; profibrotic cytokines such as IL-1 β and TGF- β) from baseline to 3 and 6 months.
2. Determine the correlation between responses at 6 months and changes in the percentage of peripheral blood T/NK-cell population (CD3-CD56+) [Treg(FoxP3+), effector T cell (CD8+T cell, CD4+ T_H1, T_H2 and T_H17 cells), CD3+, CD4-CD25+, Gr-1, Ter-119, and Antigen presenting cells (APC) APC-CD80+] from baseline to 3 and 6 months.

Section 2.0 Introduction

Chronic graft versus host disease

Chronic graft-versus-host disease (GVHD) is a major late complication of allogeneic hematopoietic cell transplantation (HCT) that affects up to 70% of HCT survivors. The syndrome is associated with major transplant-related morbidity, mortality, infectious complications, prolonged duration of immune suppression, and impaired patient-reported quality of life (2-9). Thus, it represents a major obstacle to recovery and survival following HCT, and its prevention and treatment are of significant importance. The syndrome is characterized by diverse clinical manifestations, but the most commonly affected organs are the skin, eyes, mouth, and liver.

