The 2014 NIH Biomarker Working Group Report states that the development of diagnostic and predictive biomarkers is critically necessary and represents the areas of high priority in chronic GVHD (30). In this study, we will measure the percentage of peripheral blood T/NK-cell population and the plasma levels of various proteins and cytokines (ST2, SPON1, CXCL10, IFN gamma, soluble IL-2R, IL-2, IL-6, TNF- α ; profibrotic cytokines such as IL-1 β and TGF- β) at various time points. Such assessments may allow identification of predictive biomarkers and provide insights into the biology of sclerotic chronic GVHD, and the pharmacodynamic effect of ruxolitinib in sclerotic chronic GVHD.

In a murine model, ruxolitinib reduced proliferation of effector T cells and suppression of proinflammatory cytokine production (such as TNF-alpha and IL-12p70). Further, differentiation of CD4+T cells into IFN-gamma and IL17A-producing T-cells (implicated in GVHD) was impaired (31). In patients with steroid refractory acute and chronic GVHD, responses correlated with an increase in FoxP3+ regulatory T cells, as well as a reduction in the serum levels of IL-6 and soluble IL-2 receptor (31). Zeiser et al demonstrated a decline in CD3+HLA-DR+ cells, IL-6 UNMC IRB # 333-18, Protocol Version 1.6 dated 25Jan2021

and soluble IL-2R in peripheral blood after ruxolitinib treatment (32). In myelofibrosis, the use of ruxolitinib was associated with suppression of proinflammatory cytokines such as IL-6, and TNF-alpha (33). Hence, the changes in T-cell subsets and cytokine levels correlate with GVHD activity and are associated with responses to ruxolitinib.

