10.2.4 Analysis of patient reported outcomes and Correlative data

Descriptive statistics will be computed for patient reported outcomes Lee Chronic GVHD Symptom Scale, and Scleroderma Health Assessment Questionnaire at study enrollment and 6 months. Changes in patient reported outcomes from study enrollment to 3 and 6 months will be assessed with paired t-tests or Wilcoxon sign rank test depending on whether test assumptions are met.

For **correlative studies**, changes in measured parameters from baseline to defined time points after therapy initiation will be measured. We will graphically display biomarker levels over time for each subject individually as well as averages at each time point for responders and non-responders separately. Univariate and multiple logistic regression will be used to determine if the change in biomarker level from baseline to 3 and 6 months is predictive of responder status at 6 months, looking at the biomarkers individually as well as in combination.

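### The correlative analysis puts 50 to 52 biomarker change scores into ordinary logistic regression with about 10 to 19 responders and sets no limit on predictors, selection rule, validation or multiplicity control

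*Combined protocol and SAP*

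**What the plan says.** The first objective in Section 1.4 is to "Determine the association between responses at 6 months and the changes in the plasma levels of various proteins and cytokines", from baseline to 3 and 6 months. The list opens with "ST2, SPON1, CXCR3, CXCL10, IFN gamma, soluble IL-2R, IL-2, IL-4, IL-5, IL-6, IL-12" and continues with TNF-alpha, TRAIL, IL-1 beta and TGF-beta, which makes 15 proteins. The second objective covers cell populations: CD3-CD56+, Treg, CD8+, TH1, TH2 and TH17 cells, and "CD3+, CD4-CD25+, Gr-1, Ter-119, and Antigen presenting cells (APC) APC-CD80"+. That makes 11, or 10 if CD3-CD56+ only names the group. Section 5.7 repeats both lists. The biomarker part of the Introduction (Section 2.0) gives a shorter protein list of 10, beginning "ST2, SPON1, CXCL10, IFN gamma, soluble IL-2R, IL-2, IL-6, TNF"-alpha.

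Section 10.2.4 states the method: "Univariate and multiple logistic regression will be used" to find out whether "the change in biomarker level from baseline to 3 and 6 months is predictive of responder status at 6 months". On how the markers enter these models, the plan has only one phrase: "looking at the biomarkers individually as well as in combination". It also plans graphs by subject and averages for responders and non-responders. It does not say which markers or which time point enter the combined model, how many may enter, how they are chosen, how the fit is validated, or what error level applies.

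**The concern.** There are more candidate predictors than expected responders. Without a limit or selection rule, the analyst may fit anything from a two-marker model to one with every change score. Testing each marker singly without adjustment will probably produce some nominally significant markers by chance. A combined model judged on the data that built it will look informative even when it is not.

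There is also a timing problem. Section 5.5.4 places the research blood draw and the GVHD assessment at the same month-6 visit. The change to month 6 therefore cannot forecast response at month 6; only the change to month 3 comes before the outcome.

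What is at stake is the use made of these results. The Introduction hopes that they may identify predictive biomarkers and calls that a high priority. A chance marker or an inflated AUC could be carried into later studies of sclerotic GVHD.

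**Working it through.** **Inputs.** Section 10.1 gives 42 evaluable subjects and response rates of 25% (null) and 45% (alternative). Section 1.4 gives 15 + 11 = 26 markers (25 on the narrower reading). Two changes per marker give 52 scores (50). The per-test level of 0.05 and all correlations below are assumptions.

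**The plan's own figures.** The correlative work has no sample-size statement, so the only figures to reproduce are those of the primary design. Power at 45% is the sum over x = 5 to 18 of P(X1 = x) × P(X2 ≥ 16 − x), with X1 from 18 subjects and X2 from 24. The result is 0.841, against a stated 84%. For dropout, 42 / 0.9 = 46.7, which rounds up to the stated 47.

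**Responders.** 42 × 0.45 = 18.9 and 42 × 0.25 = 10.5. Nineteen responders give 19/26 = 0.73 events per coefficient at one time point and 19/52 = 0.37 at both. At 10 events per coefficient, 19 responders support about two coefficients; 10.5 support about one.

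**Single-marker tests, no true association.**
- Expected false positives: 52 × 0.05 = 2.6, whatever the correlation. For one time point: 26 × 0.05 = 1.3.
- At least one, if independent: 1 − 0.95^52 = 0.931; for 26 tests, 1 − 0.95^26 = 0.736.
- Simulated logistic tests (19 of 42 responders, correlation 0.5 between the two time points): 93%, 91% and 74% for between-marker correlations of 0, 0.3 and 0.5.
- Simulated t-tests with correlation 0.7 over time: 90%, 81%, 68% and 50% for between-marker correlations of 0, 0.3, 0.5 and 0.7.

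**Can a combined model be fitted?** If the predictors separate responders from non-responders perfectly, the maximum-likelihood estimate is not finite. For noise predictors the function-counting theorem gives P(separation) = P(Bin(41, 0.5) ≤ p). Simulation with fixed responder counts gives similar values at 19 responders and higher ones at 11:

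| Predictors p | Formula | Simulated, 19 responders | Simulated, 11 responders |
|---|---|---|---|
| 15 | 0.059 | 0.04 | 0.22 |
| 26 | 0.970 | 0.99 | 1.00 |
| 52 | – | 1.00 | 1.00 |

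With 11 predictors the formula gives 0.002. With 2 or 4 predictors no simulated data set separated.

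**Apparent discrimination on pure noise** (42 subjects, 19 responders, mean in-sample AUC; 0.5 is no discrimination). These come from a linear score fitted by least squares, not from the planned logistic fit.
- 11 markers: about 0.80. 15 markers: about 0.85.
- Best 3 of 52 by univariate strength (correlation 0.5 over time): 0.81, about 0.79 and 0.75 for between-marker correlations of 0, 0.3 and 0.5.
- 3 markers named in advance: 0.64.

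With 11 responders the 15-marker figure rises to 0.88.

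**The case against.** The strongest reply is that the plan never says all markers enter one model. Proteins and cell populations are separate objectives, measured from separate tubes by separate assays, so combination may mean within a panel of 15 or 11. A reader might infer a single 26-marker or 52-score model that cannot be estimated. Section 10.2.4 does not support that inference, because models of panel size or smaller could usually be fitted. This part of the reply stands. It does not clear the plan, since fitted models of that size still show AUCs of about 0.75 to 0.85 on noise and nothing in the text would reveal it.

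A reader might also conclude that false leads are near certain. That needs 52 independent tests at 0.05. The two changes for a marker share one baseline value and related cytokines move together, so independence is unlikely; the plan also states no level. The accurate statement is that false leads are likely, with 2 to 3 expected by chance if no marker matters.

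On timing, the objectives in Sections 1.4 and 5.7 speak only of association or correlation. That is a fair point, and it makes the correction one of wording. Section 10.2.4 nevertheless says that the change "is predictive of responder status at 6 months" is what the regression will test, and it does not separate month 3 from month 6.

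Finally, this is correlative work, listed after the primary, secondary and exploratory objectives, and no trial decision depends on it. That limits the severity. But Section 10.2.4 does not label the results hypothesis-generating, and that label alone would not correct an inflated AUC.

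**Conclusion.** The point holds as an under-specified analysis. Its consequences depend on how the open wording is read:

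- Single tests: about 2.6 false positives in 52 if nothing is associated, with a chance of at least one of 93% under independence and roughly 50% to 91% under the assumed correlations.
- All 26 markers together: almost always no finite estimate (about 98% separation on noise).
- Panel-sized models, or 3 markers picked by univariate strength: usually estimable, but with noise AUCs of about 0.75 to 0.85, against about 0.64 for 3 markers named in advance.

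These results assume 42 subjects with complete samples, a 0.05 level, simulated noise markers and, for the AUCs, a linear score. About 19 responders is the favourable case; near 10 the overfitting is worse. The month-6 change is a concurrent association, not a prediction. This is a minor point for the trial as a whole: the primary test, the stopping rules and the safety analysis are unaffected.

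**What to change.** Revise Section 10.2.4 as follows:

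- Report univariate results with a Benjamini-Hochberg adjustment beside the nominal p-values, and state the level.
- For combinations, use penalised logistic regression (ridge or elastic net) and report a cross-validated AUC, with any marker selection done inside the folds. Alternatively, fit at most two markers named in advance, which matches about 19 responders at 10 per coefficient.
- Use only the month-3 change for prediction, and describe the month-6 change as a concurrent association.
- Label the results hypothesis-generating.
- Settle the marker list, since the Introduction names 10 proteins and Section 1.4 names 15.

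The cost is a paragraph of text and slightly more analysis work in standard software, with no new samples, visits or subjects. The downside is that fewer markers will be called significant.

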10.3 Accrual goal

It is expected that 20 subjects will be enrolled in the trial each year. To meet the accrual goals of 47, we require approximately 2.5 years of enrollment with 2 years of follow up.

10.4 Stopping rule

Serious adverse events and deaths will be reviewed by the study team and principal investigators on an ongoing basis.

The risk of treatment-related mortality is 10-20% in patients with steroid refractory chronic GVHD (15, 42). The study will have continuous mortality monitoring, and if $\geq 20\%$ have treatment-related mortality that is possibly, probably or definitely related to the study drug, accrual will be halted (see stopping rules below). Subjects, who are already enrolled in the study, and are tolerating the study drug may continue the drug at the discretion of the treating physician.

Continuous monitoring (43) will be performed after each subject has received the first dose of ruxolitinib, beginning when the 2nd subject has received the first dose of ruxolitinib, with K=47 interim analyses, a null hypothesis mortality rate of 0.10, an alternative hypothesis of 0.20, and power of 0.80. The sample size is too small to control alpha and power simultaneously, so alpha is 0.19 to allow for 80% power (see below table for operating characteristics). The table below displays the boundaries b_k for each interim analysis k. If the observed number of treatment-related mortality is greater than b_k , accrual will be terminated. Stopping boundaries were calculated with the R package “clinfun” based on Ivanova (41), using this code: toxbdry(0.1, 0.2, 3:47, cP0=0.1, cP1=0.8, priority="alt").

Continuous monitoring boundaries for K=47 when the true mortality rate is 0.10 and the alternative hypothesis is 0.20 and alpha=0.05, 80% power

Stop if treatment-related mortality is greater than or equal to the boundary ($\geq b_k$)

K	1	2	3	4	5	6	7	8	9	10	11	12	13	14	15	16	17	18	19	20	21	22	23
b_k	-	2	2	2	2	2	2	2	2	3	3	3	3	3	4	4	4	4	4	4	4	4	5

K	24	25	26	27	28	29	30	31	32	33	34	35	36	37	38	39	40	41	42	43
b_k	5	5	5	5	5	5	6	6	6	6	6	6	6	6	7	7	7	7	7	7

K	44	45	46	47
b _k	7	8	8	9

Operating characteristics of the stopping rule

P(death)	P(stopping)	Expected sample size
0.10	0.192	41.1
0.12	0.309	37.8
0.14	0.443	34.1
0.16	0.577	30.2
0.18	0.697	26.4
0.20	0.795	22.9

All grade 3 and above or serious adverse events recorded during the study will be summarized. Listings of deaths, serious adverse events, and adverse events leading to early termination of study treatment or premature withdrawal from study will also be provided to the DSMC.

Section 11.0 Records to be Kept

Information regarding the actual treatments, adverse events, and laboratory tests are to be recorded on appropriate forms. See attached Data forms. Serious adverse events, when noted, will be recorded on site via the standard serious adverse effects form.

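### Section 10.4 gives two non-equivalent mortality criteria for halting accrual, a 20% observed proportion and a boundary table, and the printed operating characteristics match neither

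*Combined protocol and SAP*

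**What the plan says.** All of this is in protocol section 10.4 (Stopping rule).

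- The halting sentence, under continuous mortality monitoring: "if $\geq 20\%$ have treatment-related mortality that is possibly, probably or definitely related to the study drug, accrual will be halted". It then refers the reader to the rules below. It attaches no minimum number of subjects or deaths to the 20%.
- The look schedule: monitoring after each dosed subject, "beginning when the 2nd subject has received the first dose of ruxolitinib, with K=47 interim analyses". The quoted software call uses looks 3 to 47.
- The design rates: "a null hypothesis mortality rate of 0.10, an alternative hypothesis of 0.20, and power of 0.80".
- The boundary, in the text: "If the observed number of treatment-related mortality is greater than b_k , accrual will be terminated". In the table caption: "Stop if treatment-related mortality is greater than or equal to the boundary".
- The error rate, in the text: "so alpha is 0.19 to allow for 80% power". In the caption: "the alternative hypothesis is 0.20 and alpha=0.05, 80% power".
- The printed operating characteristics: probability of stopping 0.192 at 10% mortality (expected sample size 41.1) and 0.795 at 20% (expected sample size 22.9).

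**The concern.** The cross-reference presents the 20% sentence and the table as one rule. A constant observed proportion and a count boundary derived from testing 0.10 against 0.20 are not the same thing. The 0.20 is the mortality rate at which the design wants a high chance of stopping; it does not follow that accrual stops when the observed proportion reaches 0.20.

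This is the trial's only numeric mortality stopping rule. At some counts, people reviewing deaths would get opposite instructions from the same section. Early on, the sentence can halt accrual after a single possibly related death when the table does not. Late in accrual, the table as captioned stops at counts the sentence lets pass. The printed operating characteristics are supposed to tell the reader how often each kind of error happens, so it also matters which rule they describe.

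**Working it through.** **Inputs, all from section 10.4:** at most 47 subjects; a look after each subject from the 2nd; the printed b_k; the 20% proportion; true mortality p of 0.10 and 0.20. Each outcome is assumed known before the next look.

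**Thresholds.** The sentence halts at look k when deaths/k ≥ 0.20, that is, at ceil(0.2k) deaths.

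| Rule | Deaths needed (looks k) |
|---|---|
| 20% sentence | 1 (2–5), 2 (6–10), 3 (11–15), 4 (16–20), 5 (21–25), 6 (26–30), 7 (31–35), 8 (36–40), 9 (41–45), 10 (46–47) |
| Table, read as ≥ b_k | 2 (2–9), 3 (10–14), 4 (15–22), 5 (23–29), 6 (30–37), 7 (38–44), 8 (45–46), 9 (47) |

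They differ at k = 2–5, 10, 15, 21–22, 26–29 and 31–47: 4 + 1 + 1 + 2 + 4 + 17 = 29 of 46 looks. The table needs more deaths at 6 of these (k = 2–5, 10, 15) and fewer at 23. Examples:

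- k = 5: 1/5 = 20%, so the sentence halts; b_5 = 2, so the table does not.
- k = 44: 7/44 = 15.9%, so the sentence does not halt (it needs 9); b_44 = 7, so the table as captioned does.

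Read as > b_k, the table's threshold is b_k + 1, and the two differ at 30 of 46 looks. The conflict therefore does not depend on the inequality.

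**Probability of stopping.** Let g_k(s) be the probability of s deaths after k subjects with no stop so far, and c_k the threshold. Then

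f_k(s) = (1 − p)·g_{k−1}(s) + p·g_{k−1}(s − 1),

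the probability of stopping at k is the sum of f_k(s) over s ≥ c_k, and g_k(s) = f_k(s) for s < c_k. P(stop) is the sum over k, and E(N) = Σ k·P(stop at k) + 47·(1 − P(stop)).

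**The plan's own figure first.** The printed 0.192 and 0.795 cannot be reproduced from the printed table under either inequality, as the rows below show. A stand-in boundary (an assumption: repeated pointwise tests of 0.10 at looks 3 to 47, stopping when the count exceeds the limit) gives 0.192 and 0.798 with expected sizes 41.1 and 22.9. The printed figures therefore appear to belong to a boundary other than the one tabulated.

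| Rule | P(stop), 10% | P(stop), 20% | E(N), 10% | E(N), 20% |
|---|---|---|---|---|
| Printed in 10.4 | 0.192 | 0.795 | 41.1 | 22.9 |
| Table, ≥ b_k | 0.366 | 0.896 | 34.6 | 15.9 |
| Table, > b_k | 0.149 | 0.762 | 42.9 | 25.6 |
| 20% sentence, looks from k = 2 | 0.498 | 0.883 | 26.1 | 11.1 |
| Sentence or table (≥ b_k), whichever comes first | 0.534 | 0.929 | 25.5 | 10.3 |

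**Sensitivity to the first look.** At 10% mortality, the chance of at least one death among the first five is 1 − 0.9^5 = 0.410, so most of the 0.498 arises there. Any first look from k = 1 to 5 gives the same 0.498, because one death in the first five is still at least 20% at k = 5. The text's 2nd subject and the code's 3rd therefore give the same P(stop). For later starts, P(stop) at 10% is 0.333 from k = 6, 0.236 from k = 12 and 0.171 from k = 20. Read once at k = 47 it is P(X ≥ 10 | 47, 0.10) = 0.016, and at 20% mortality 0.471.

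**The case against.** The strongest defence is that the 20% sentence only introduces the table in words. It points to the rules below, sets no look schedule of its own, uses the alternative-hypothesis rate, and is followed by a full operational rule. That may well be the intent. But the sentence is an operative instruction in a safety rule, no text subordinates it to the table, and as a summary it is inaccurate: from k = 31 on, every captioned boundary lies below 20% (for example 6/37 = 16.2%). The need to reconcile stands even if the wording was only loose.

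Two further objections limit the size of the point.

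- The 0.498 applies the stated look schedule to the sentence and is driven by the first five subjects. This is right, and the sensitivity figures show how far it falls with later starts. No later start or minimum denominator is in the plan, however.
- A reader might infer that following the sentence raises the false-stop probability from the printed 19% to about half. The documents do not support that contrast, because the printed table does not deliver 0.192 either. Against the table as captioned the gap at 10% mortality is 0.498 − 0.366 = 0.132. At 20% mortality the sentence stops slightly less often than the captioned table (0.883 against 0.896).

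Nor does it follow that the two criteria cannot be used together. Halting on whichever comes first is feasible; it simply has operating characteristics (0.534 and 0.929) that the plan does not report.

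**Conclusion.** Section 10.4 contains two different numeric rules for the same decision. They conflict at 29 of 46 looks (30 under the strict inequality), in both directions, and the threshold comparison needs no modelling assumption. The stopping probabilities rest on immediately known outcomes, a constant mortality rate and looks after every subject from the 2nd; the 0.498 in particular should be quoted with its dependence on the early looks. The printed 0.192 and 0.795 describe neither the sentence, nor the table under either inequality, nor the combination. The defect is one of internal consistency, together with operating characteristics that do not belong to a stated rule. It does not show which stopping rule is the appropriate one.

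**What to change.** Reconcile section 10.4 so that it states one halting criterion, one inequality direction and one first look.

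- If the table is the rule: remove the 20% halting clause, keep 0.20 only as the alternative-hypothesis rate, and make the text and caption agree on whether accrual stops at b_k or above it.
- If the proportion is the rule: remove the table and state the first look at which the proportion applies.

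In either case, recompute and reprint the probability of stopping and the expected sample size for the rule kept, and make the stated alpha agree with them (the text has 0.19, the caption 0.05).

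The cost is a short text edit and a recalculated table, with no extra subjects or data. The price is that the stated figures may look worse: keeping the table as captioned would replace 0.192 by 0.366 at 10% mortality, while reading it as > b_k gives 0.149 but a stopping probability of 0.762 at 20%, below the stated 80% power.

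### The mortality boundary in section 10.4 does not produce its own printed operating characteristics, and after the 47th first dose a crossing triggers nothing

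*Combined protocol and SAP*

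**What the plan says.** All of the following is in section 10.4 of the combined protocol and SAP unless another section is named.

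- **When the boundary is checked.** Monitoring "will be performed after each subject has received the first dose of ruxolitinib, beginning when the 2nd subject has received the first dose", with 47 looks, a null mortality of 0.10 and an alternative of 0.20.
- **What a crossing does.** It terminates accrual. A separate sentence on 20% or more related mortality gives the same action: "accrual will be halted (see stopping rules below". Subjects on drug are dealt with by "Subjects, who are already enrolled in the study, and are tolerating the study drug may continue the drug at the discretion" of the treating physician.
- **Sign.** The text reads "If the observed number of treatment-related mortality is greater than" b_k. The table heading reads "Stop if treatment-related mortality is greater than or equal to the boundary".
- **Error rate.** The text says the sample is too small to control both error rates, "so alpha is 0.19 to allow for 80% power". The table title gives alpha as 0.05. The operating-characteristics table gives P(stopping) 0.192 at 10% and 0.795 at 20%, with expected sample sizes 41.1 and 22.9.
- **Length of dosing.** Sections 5.1 and 5.4 give 6 months, or 12 with the extension, then a one-month taper.
- **Other oversight.** "Serious adverse events and deaths will be reviewed by the study team and principal investigators on an ongoing basis". Sections 9.0 and 9.2.2 send deaths, serious adverse events and grade 3 or higher events to the DSMC.

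**The concern.** A stopping rule needs one threshold, one sign, and error rates that belong to that threshold. Here a site or the DSMC cannot tell whether, for example, the second or the third related death among the first nine subjects stops accrual. The error rates that were approved belong to neither reading.

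The second issue is reach. Looks happen only at first doses, and the only lever is accrual. After the 47th first dose there is no accrual left to stop, but the last subject may still have 7 months of drug ahead (6 plus taper) or 13 (12 plus taper). Even when the rule fires during accrual, the protocol does not ask any body to record a decision on those still on drug or on new extension entries. A treating physician sees one patient who is tolerating treatment; a crossing is information about the whole trial.

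**Working it through.** **1. Reproducing the printed operating characteristics.** Inputs are the printed b_k for k = 2 to 47. Let f_k(x) be the probability of x related deaths after k subjects without having stopped:

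f_k(x) = (1 − p)·f_{k−1}(x) + p·f_{k−1}(x − 1)

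At each k, the probability at or beyond the boundary is removed and added to P(stop). Expected N is the sum of k × P(stop at k), plus 47 × P(never stop). Each outcome is taken as known at its look.

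| | P(stop), 10% | P(stop), 20% | Expected N, 10% | Expected N, 20% |
|---|---|---|---|---|
| Printed table | 0.192 | 0.795 | 41.1 | 22.9 |
| Printed b_k, ≥ | 0.366 | 0.896 | 34.6 | 15.9 |
| Printed b_k, > | 0.149 | 0.762 | 42.9 | 25.6 |

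Neither sign reproduces the table. The ≥ reading can be ruled out by hand. Since b_k = 2 for k = 2 to 9, the chance of stopping by subject 9 at 10% mortality is 1 − 0.9^9 − 9 × 0.1 × 0.9^8 = 1 − 0.3874 − 0.3874 = 0.225. That already exceeds the 0.192 printed for the whole trial.

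**2. A boundary that does match.** As an illustration, for k = 3 to 47 let b_k be the smallest count whose Binomial(k, 0.10) upper tail is at most 0.079, and stop at ≥ b_k. This gives 0.190 and 0.795, with expected N 41.1 and 22.9. The boundaries are 2 (k = 3–4), 3 (5–10), 4 (11–16), 5 (17–23), 6 (24–30), 7 (31–37), 8 (38–45) and 9 (46–47). The printed operating characteristics therefore appear to belong to a different boundary from the printed one.

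**3. What looks at first doses miss.** The documents give no timing of deaths, so this step is a simulation under stated assumptions. There are 47 subjects at 20 per year (section 10.3), one every 12/20 = 0.6 months. Courses last 7 months (none extend) or 13 months (all extend). Each subject has a related death with probability p during the course. Death times are uniform over the course, or front-loaded (squared-uniform). A trial is missed if no look fires but related deaths reach the k = 47 boundary of 9.

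With the recalculated boundary, the missed share is:

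- 20% mortality, uniform: 8.5% (none extend) to 22.6% (all extend)
- 20% mortality, front-loaded: 4.6% to 11.9%
- 10% mortality, uniform: 1.1% to 2.5%

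These shares are what late checks would add.

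**4. The whole package against the rule as printed.** Share of trials in which the rule fires at 20% mortality:

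| Death times, extension | Printed ≥, first doses only | Printed >, first doses only | Recalculated ≥ plus late checks |
|---|---|---|---|
| Uniform, none extend | 74.1% | 55.9% | 67.5% |
| Uniform, all extend | 56.7% | 37.7% | 63.5% |
| Front-loaded, none | 79.7% | 62.7% | 70.7% |
| Front-loaded, all | 70.3% | 51.1% | 66.8% |

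The package fires less often than the printed ≥ rule in three of four scenarios, and more often than the printed > rule in all four.

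**5. Subjects on drug at a crossing.** With the printed ≥ boundaries at 20% mortality, 9 to 17 subjects are on drug when the rule fires (8 to 14 front-loaded). Expected later related deaths among them are 1.1 to 2.0 (0.7 to 1.2 front-loaded).

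**The case against.** **Oversight does not end with the 47th first dose.** A reader might infer that nobody watches mortality from then on. The documents do not support that:

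- Individual stopping criteria apply throughout (sections 5.2 and 5.6), and the study team reviews deaths on an ongoing basis (10.4).
- The DSMC receives deaths and serious events and recommends its own monitoring frequency (9.0, 9.2.2).
- The IRB hears of unexpected fatal events within 24 hours and expected ones within 10 business days (9.2.1).
- The supplier hears of every serious event within 24 hours, and suspected unexpected serious reactions go to the health authority (9.2.3).

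This stands. What is missing is a count that requires a recorded decision. The DSMC's own policy, which is outside the documents, may already contain one.

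**The wording "The study will have continuous mortality monitoring" may mean that every death is checked.** Perhaps so, but the stated action is still on accrual and is empty once 47 are dosed.

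**Continuation is a deliberate choice.** A reader might infer that letting tolerating subjects continue is itself a fault. Sections 5.1 and 5.2 explain that this population has few options, and the choice is not contested.

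**The scenario is remote.** Section 2.0 reports one-year survival of 92.7% in a retrospective ruxolitinib series. If all 100 − 92.7 = 7.3% mortality were drug-related, the missed share with the recalculated boundary would be only 0.1% to 0.4%. This stands as a limit on size. The 20% rate is the rule's own alternative, not a forecast.

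**The fix may trigger fewer reviews.** Against the printed ≥ rule it usually does, as the second table in the working shows. That extra sensitivity comes with a stopping probability of 0.366 at 10% mortality, about twice the stated 0.19.

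**Conclusion.** The point holds in two parts of different strength.

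The firm part is that section 10.4 is wrong as written: two signs, two alphas, and boundaries that give the printed operating characteristics under neither sign. This rests on exact calculation from the printed table.

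The softer part is a gap in reach. A crossing acts only on accrual, does nothing after the 47th first dose, and never requires a trial-level decision on continued dosing or extension entry. Its size depends on assumed death timing, even accrual and the share extending. The largest figure, 23 points, needs 20% related mortality, uniform death times and every subject extending. The last is an upper bound, because section 5.1 makes subjects progressing at 6 months stop.

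Two stronger conclusions should not be drawn. The documents do not show that deaths would be averted: the 1.1 to 2.0 later deaths are only a ceiling on what a dosing decision could affect. Nor does the full package trigger review more often than every reading of the present rule. Its gain is consistent error rates and a defined response after accrual closes.

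**What to change.** Amend section 10.4 as follows.

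1. Rerun the boundary code. Use one sign and one alpha throughout, and print the boundaries with the operating characteristics that belong to them. State the first look consistently: the text starts at the 2nd subject, the printed code at the 3rd.
2. After the 47th first dose, compare the count with the k = 47 boundary (9 in the illustrative recalculation, with ≥) at each death possibly, probably or definitely related to study drug. Continue until 30 days after the last subject's last dose.
3. Refer any crossing, and each related death after a crossing, promptly to the existing DSMC. It records a decision on continued dosing and on new extension entries, and stays free to let tolerating subjects continue.

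The amendment should list the existing safeguards so that the trigger is read as an addition to them. If the DSMC policy already holds an equivalent trigger, a cross-reference would serve for item 3.

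The cost is one rerun of the code and about three sentences, using a committee and death reports already in place. The downside is an occasional unscheduled DSMC review. At 10% mortality the late checks add about 1 to 2.5 percentage points of such reviews under uniform death times.
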